5.3 What are the research questions or hypotheses to be studied?

Hypothesis #1:

A low-carbohydrate Diabetes Prevention Program (LC-DPP) will be feasible and acceptable among Veterans with prediabetes?

Hypothesis #2:

A LC-DPP can help more Veterans with prediabetes to achieve at least 5% body weight loss compared to existing lifestyle change programs (e.g., MOVE!)

5.4 Describe the relevance to Veterans of studying the stated research questions or hypotheses and the importance of the knowledge this protocol is likely to generate:

Twenty-five percent of Veterans have type 2 diabetes and an estimated 28% have prediabetes, an asymptomatic state characterized by abnormal blood glucose levels and an elevated risk of type 2 diabetes. Modest weight loss (i.e., at least 5%) can substantially reduce the risk of progression from prediabetes to type 2 diabetes. Behavioral change programs for weight loss are available within the VA, but most participants do not achieve clinically-significant weight loss.

Novel and scalable strategies are needed to help more Veterans with prediabetes to lose weight. Through this study, we will demonstrate the feasibility and acceptability of a LC-DPP among Veterans with prediabetes. These data will inform a large-scale comparative effectiveness trial of LC-DPP versus VA-MOVE.

5.5 What is the estimated duration of the entire protocol? (From IRB approval to IRB closure)

2 years

5.6 Check one of the boxes below based on your study design:

- Prospective Study
- Retrospective Study
- Both

Other

5.7 What research methods will be used in the protocol? (Check all that apply)

- Surveys/Questionnaires
- Behavioral Observations
- Focus Groups
- Control Group
- Specimen Collection
- Interviews
- Chart Reviews
- Randomization
- Placebo
- Deception
- Audio Recording
- Video Recording
- Double-Blind
- Withhold/Delay Treatment
- Other (Specify)

Other:

5.8 Indicate whether or not each of the following applies to this protocol:

Does the Protocol involve international research?

NOTE: International research does not include studies in which VA is only one of multiple participating sites where the overall study-wide PI is not a VA Investigator.

Yes No

The protocol includes interaction between research staff (or clinicians acting on behalf of the researchers) and human subjects.

Yes No

This protocol involves the use of retrospective data, including, but not limited to, data from CDW and CMS.

Yes No

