6.58 RETROSPECTIVE DATA USE

6.59 Describe in detail all sources of retrospective data that will be used by the protocol.

Retrospective data will be used for screening only. Data from VA medical records will be obtained via the Clinical Data Warehouse (CDW) to identify patients with prediabetes. We will look at data for patients seen at VAAAHS in the past year (May 2019- May 2020). We will not review identified data of individuals in the VA MOVE program. Rather, there have been many published reports of VA MOVE program outcomes and we will compare our data with published VA MOVE! data as well as data from similar programs (e.g., Center for Disease Control and Prevention's National Diabetes Prevention Program).

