3.0 Objectives

In this mixed methods pilot study, we aim to test whether a LC-DPP is feasible to deliver in the VA Health System. We hypothesize a LC-DPP will lead to greater participation and weight loss than VA MOVE! In addition to objective measures of this program's preliminary efficacy (e.g. weight, HbA1c) we will also obtain qualitative participant feedback on the intervention. Taken together, these data will be used to improve the curriculum and inform larger-scale interventions.

Aim 1: To evaluate acceptability and feasibility of delivering a Low-Carb Diabetes Prevention Program in the VA Health System

The VA Health System has an established infrastructure to deliver group-based lifestyle programs including VA MOVE! We will deliver a VA LC-DPP that was piloted at a Michigan Medicine primary care clinic in 2017. We will collect data on participant recruitment, session attendance, and intervention satisfaction to assess the acceptability of a VA LC-DPP. Qualitative feedback from VA diabetes educators, primary care providers and LC-DPP participants will be collected to better understand barriers and facilitators of a VA LC-DPP and identify challenges to scalability.

Aim 2: To estimate weight loss from a Diabetes Prevention Program that is modified to incorporate a Low Carbohydrate (LC-DPP) rather than the traditional low fat diet among veterans with prediabetes. We will conduct a single-arm mixed methods pilot study to estimate weight loss as well as the percentage of participants who achieve 5% weight loss in a 16-week LC-DPP. Weight loss from the pilot LC-DPP cohort will be compared to weight loss

outcomes from previously published VA DPP and VA MOVE! studies. We will also evaluate secondary outcomes including change in physical activity, neuropathy symptoms, hemoglobin A1c, triglycerides, cholesterol and HDL over the 12- month study period.

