5.0 Study Procedures

5.1 Study Design

We will conduct a single-arm mixed methods pilot study to test the preliminary efficacy on weight loss of a LC-DPP among Veterans with prediabetes (as defined by the American Diabetes Association [ADA] ²⁴). We hypothesize that at least 50% of LC-DPP participants will achieve at least 5% weight loss at 12 months and that the average weight loss in the LC-DPP will be greater than the average weight loss among historical controls in VA MOVE!.¹¹

Our team previously adapted the Centers for Disease Control and Prevention's (CDC's) National Diabetes Prevention Program (NDPP) curriculum—a lifestyle change program similar to MOVE!—to teach participants to follow a low-carbohydrate rather than a low-fat diet. We pilot tested our low-carbohydrate Diabetes Prevention Program (LC-DPP) among adults with prediabetes at a single, academic medicine primary care clinic.

The LC-DPP curriculum was adapted from the CDC National Diabetes Prevention Program materials and consists of 16 weekly one-hour group sessions over first 6 months (i.e. core phase) and 8 one-hour group sessions once or twice a month over the next 6 months (i.e. maintenance phase). Importantly, our adapted curriculum will adhere to the CDC's Diabetes Prevention Recognition Program (DPRP) guidelines, which aim to maintain the integrity of the DPP in heterogeneous settings. The DPRP formally recognizes sites that achieve specific targets (e.g. session attendance, weight loss) through use of a CDC-approved curriculum. Therefore, our curriculum, if effective, may be eligible for CDC-approval, which would facilitate future dissemination of this intervention.

We will use a mixed-methods sequential explanatory design, which is to say that quantitative data and qualitative data will be collected in two consecutive phases within the study ²⁵. Specifically, in the first phase, we will collect and analyze the quantitative data (e.g. surveys, weight, A1c, lipids). In the second phase, we will collect and analyze qualitative data (e.g. semi-structured interviews). The rationale for this approach is that the quantitative data will provide a general overview of the intervention's efficacy and limitations, and the qualitative data will help to explain these findings by exploring participants' experiences and perspectives in more depth.

Intervention

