5.6 Data Analysis

Quantitative analysis

Descriptive statistics will be used for baseline survey response data including demographic and socioeconomic characteristics. For all continuous outcomes, we will calculate mean change and standard deviation from baseline to 6 months and 12 months and compare outcomes from baseline to 6 months and 12 months using paired *t*-tests. For all categorical outcomes, we will

use chi-square or Fisher's exact tests to examine changes from baseline to 6 and 12 months. All analyses will be conducted using Stata 14.

Qualitative analysis:

Semi-structured interviews will be recorded and transcribed verbatim. Interviews will then be imported into qualitative analysis software. Two investigators will independently read and code transcribed interviews. Interviews will then be coded jointly using consensus conferences. Interviews will be analyzed using directed content analysis²⁷, which is to say that codes will be created to reflect the main topics in the interview guide and to characterize the patterns and themes that emerged from the data.²⁸

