Low-Carbohydrate Diabetes
Prevention Program Among
Veterans With Prediabetes (VA LC-
DPP)

Prepared for ClinicalTrials
Resubmission 4/20/21

Statistical Analysis Plan:

Quantitative analysis

Descriptive statistics will be used for baseline survey response data including demographic and socioeconomic characteristics. For all continuous outcomes, we will calculate mean change and standard deviation from baseline to 6 months and 12 months and compare outcomes from baseline to 6 months and 12 months using paired t-tests. For all categorical outcomes, we will use chi-square or Fisher's exact tests to examine changes from baseline to 6 and 12 months. All analyses will be conducted using Stata 14.

Qualitative analysis:

Semi-structured interviews will be recorded and transcribed verbatim. Interviews will then be imported into qualitative analysis software. Two investigators will independently read and code transcribed interviews. Interviews will then be coded jointly using consensus conferences. Interviews will be analyzed using directed content analysis²⁷, which is to say that codes will be created to reflect the main topics in the interview guide and to characterize the patterns and themes that emerged from the data.²⁸

**Cravings:
Control of Eating Questionnaire**

Over the past 7 days...

How strong was your desire to eat sweet foods?	Q1	Answer choices on a sliding scale from 0 to 100 with anchors at 0 and 100:	Items on the CoEQ are assessed by 100 mm VAS with items relating to each subscale being averaged to create	Dalton M, Finlayson G, Hill A, Blundell J. Preliminary validation and principal components analysis of the Control of
How strong was your desire for non-	Q2	0- not at all strong 10 20	to create	

Over the past 7 days, how often have you had cravings for

Sweet foods like	Q3	Answer choices	
Other sweet foods (cakes, pastries, cookies, etc)?	Q4	on a sliding scale from 0 to 100 with anchors at 0 and 100:	
Fruit or fruit juice?	Q5	0- not at all	
Dairy foods (cheese, yogurts, milk, etc)?	Q6	10 20 30 40 50 60 70 80 90 100-	
Starchy Foods that are not sweet like French fries, potato chips,	Q7 Q8	70 80 90 100- extremely often	

Stress Eating

Please indicate how you usually experience a stressful event

I eat more of my favorite foods to	Q1	Answer choices 1 through 4 with anchors on 1 and 4:	Reverse code and sum, so that higher scores indicated	Tsenkova, V., Boylan, J. M., & Ryff, C. (2013). Stress
------------------------------------	----	---	---	--

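### The weight-loss hypotheses are set against 50% and against MOVE!, but the only planned tests are against baseline; the share losing 5% needs an exact interval and stated denominators

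*Protocol*

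**What the plan says.** **Hypotheses.** Protocol narrative 5.1: "We hypothesize that at least 50% of LC-DPP participants will achieve at least 5% weight loss at 12 months". The same sentence adds that average loss will exceed that of historical MOVE! controls. IRB application 5.3, Hypothesis #2: "A LC-DPP can help more Veterans with prediabetes to achieve at least 5% body weight loss compared to existing lifestyle change programs", with MOVE! as the example.

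**Aim and comparison.** Aim 2 (narrative 3.0) is to estimate weight loss and "the percentage of participants who achieve 5% weight loss in a 16-week LC-DPP", and to compare weight loss with "outcomes from previously published VA DPP and VA MOVE! studies". IRB application 6.59 repeats the promise: "we will compare our data with published VA MOVE! data as well as data from similar programs", naming the National DPP.

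**Analysis.** Besides mean change with SD, the SAP says it will "compare outcomes from baseline to 6 months and 12 months using paired t-tests". Its categorical rule is: "For all categorical outcomes, we will use chi-square or Fisher's exact tests to examine changes from baseline to 6 and 12 months". Narrative 5.6 has the same text. Neither gives a confidence interval, an analysis against 50%, or a method for the MOVE! comparison.

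**Status of the outcome.** The narrative abstract lists achievement of at least 5% loss as a secondary outcome. Feasibility and acceptability are primary.

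**Time points and missing weights.** Narrative 5.5 computes percent loss at 6 and 12 months and plans catch-up weigh-ins for people who miss sessions. IRB application 9.7 keeps data from before withdrawal. Both 9.7 and narrative 5.7 bar collection afterwards. No section says how a missing 12-month weight counts in the 5% share.

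**The concern.** A test against baseline asks whether anything changed. The hypotheses ask whether the share reaches 50% and whether results exceed MOVE!. The planned tests can be significant without bearing on either question.

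The mismatch is sharpest for the 5% outcome, which has no baseline value other than zero. A chi-square or Fisher test of baseline against follow-up also treats two measurements on the same people as independent groups.

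Narrative 3.0 says the pilot's data, taken together, will inform larger interventions, and the abstract names a comparative effectiveness trial against MOVE!. The designers of that trial need a share and a mean with their uncertainty and a known denominator. A p-value against zero gives them little. The unstated denominator matters because a share among those weighed will be too high if people who did not lose weight are weighed less often.

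**Working it through.** The documents contain no precision or power calculation, so there is no figure of the plan's own to reproduce.

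**Inputs**
- n = 30: the recruitment maximum (narrative 5.1, Intervention).
- n = 22: 220 letters × 10% expected enrolment (narrative 5.2).
- MOVE!: 15-18% reach 5% loss; mean loss 0.13-3.3 kg over one year (narrative 2.0).
- Target: 50% at 12 months (narrative 5.1).
- Assumed, because not stated: two-sided 5% level, 95% intervals, SD of weight change 4-8 kg, 10-40% of 12-month weights missing.

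**1. The categorical rule read literally.** For 0/n against k/n the two-sided Fisher p-value is 2 × C(n,k) / C(2n,k). The exact (Clopper-Pearson) limits are the 2.5% quantile of Beta(k, n−k+1) and the 97.5% quantile of Beta(k+1, n−k).

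| n | k | Share | Fisher p | Exact 95% CI |
|---|---|---|---|---|
| 30 | 5 | 17% | 0.0522 | |
| 30 | 6 | 20% | 0.0237 | 7.7-38.6% |
| 22 | 4 | 18% | 0.1078 | |
| 22 | 5 | 23% | 0.0485 | 7.8-45.4% |

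For example, at n = 30 and k = 6: 2 × 593,775 / 50,063,860 = 0.0237. At the first significant result for either n, the interval contains 15-18% and excludes 50%.

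Respecting the pairing does not help. Exact McNemar gives p = 2 × 0.5^k, which is 0.031 for k = 6 and 0.0625 for k = 5, and it still tests only against zero.

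**2. The other reading.** If the rule is limited to items with a baseline value, step 1 does not apply. The 5% outcome is then a bare percentage.

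**3. Mean weight.** A paired t-test is significant once mean change exceeds t(0.975, n−1) / √n SDs: 0.37 SD at n = 30 and 0.44 SD at n = 22. With SD 4-8 kg that is 1.5-3.0 kg and 1.8-3.5 kg. All but the top of the second range lies within the 0.13-3.3 kg cited for MOVE!.

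**4. What an interval would show.** An observed 50% gives 31.3-68.7% (15/30) or 28.2-71.8% (11/22). Both lie above 18%. Both are consistent with a true share of 50%, but neither demonstrates that the true share is at least 50%.

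**5. Denominator, illustration only, 30 enrolled.**

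| Missing | Achievers / weighed | Achievers / all enrolled |
|---|---|---|
| 3 | 14/27 = 52% | 14/30 = 47% |
| 6 | 12/24 = 50% | 12/30 = 40% |
| 9 | 11/21 = 52% | 11/30 = 37% |
| 12 | 9/18 = 50% | 9/30 = 30% |

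In the second row, if 2 of the 6 unweighed people had a last recorded loss of at least 5%, using last recorded weights gives 14/30 = 47%.

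**6. Time point.** Narrative 5.1 names 12 months, Aim 2 describes a 16-week program, and narrative 5.5 uses 6 and 12 months. Narrative 5.1 spreads the 16 core sessions over the first 6 months, and IRB application 6.26 aligns sessions 16 and 24 with the 6- and 12-month blood draws.

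**The case against.** **The Fisher result depends on a literal reading.** Achieving 5% loss is itself a change, so the authors may have meant the rule only for items that have a baseline value. This is fair, and step 1 is conditional on the literal reading. But the rule says it covers all categorical outcomes, and the narrower reading leaves a named secondary outcome without inferential analysis.

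**The aim is estimation, in a small single-arm pilot.** This also stands: no power calculation or success threshold is called for. It favours an interval, which is the natural output of estimation and is not planned.

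**A reader could compute the intervals from mean, SD, n and k/n.** True once those are reported, but which n and k belong in the share is exactly what is unstated. Nor does it rescue a named test that cannot address the hypotheses.

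**Counting missing as not achieved is only a convention.** Agreed. It may not match how the published rates were computed; narrative 2.0 gives no denominator for the 15-18%. It should be one of the figures shown, not the only one.

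**Stronger readings to avoid.** A reader might infer that the study will claim superiority over MOVE! from a p-value against zero. Nothing in the documents says so; the comparison is promised without a method. A reader might infer that a weighed-only analysis is planned. The documents are silent on the denominator, plan catch-up weigh-ins and keep pre-withdrawal data. A reader might also see a hard conflict over the time point. Session 16 falls at 6 months and the hypothesis itself names 12, so the 16-week phrase is mostly loose wording.

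**Conclusion.** The point holds, as a moderate and inexpensive correction. The planned inferential analyses do not address either weight reference that the protocol sets. On the literal reading, the test of the 5% outcome can be significant at 20% (n = 30) or 23% (n = 22), which is compatible with the cited MOVE! share and against the study's own 50% hypothesis. On the narrower reading, that outcome has no inferential analysis.

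The Fisher and exact-interval figures rest on n = 30 or 22 and a two-sided 5% level. The kilogram thresholds rest on the assumed SDs. The missing-weight figures are invented to show sensitivity; the actual size of any bias is unknown. The comparison with 15-18% takes that range as narrative 2.0 reports it.

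**What to change.** 1. In the SAP and narrative 5.6, exempt the 5% outcome from the baseline chi-square/Fisher rule. Report the 12-month share with an exact (Clopper-Pearson) 95% CI, and mean weight change with a 95% CI. Set both descriptively beside 50%, the MOVE! figures (15-18%; 0.13-3.3 kg) and the published DPP figures, without pass/fail cut-offs. State that the comparison is historical and non-randomised.
2. Report the share over all enrolled and over those weighed, side by side, with both denominators shown. Counting a missing weight as not achieved is a reasonable convention for the all-enrolled figure. A last-recorded-weight version can use the data kept under IRB application 9.7.
3. Reconcile the 16-week wording of Aim 2 with the 12-month hypothesis in narrative 5.1 and the 6- and 12-month outcomes in narrative 5.5.

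The cost is a few sentences and minutes of analysis, with no new data. The downside is that the reported share may look less favourable and its denominator may differ from that of the published rates, which is why both denominators should be visible.

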13.9 VA SENSITIVE DATA (VASI)

13.10 Please describe your use of VA Sensitive Information (VASI):

- This protocol does not collect or use VASI
- This protocol uses, but does not save, collect, copy, or record VASI.
- This protocol collects, records, or saves VASI.

In which of the following ways will VASI be accessed/collected?

- Computer access
- Medical chart review
- Patient treatment
- Personal interviews
- Other

Please give a brief description of the data sources mentioned above and how they will be accessed.

Medical charts will be used to identify patients who meet study eligibility criteria and also to order and record laboratory tests (i.e., HbA1c, lipid panel). Study participants will be invited to take part in optional semi-structured interviews at 6 and 12 months. Participants will complete surveys at baseline, 6 months, and 12 months; these surveys will include self-reported side effects and experiences with the intervention.

13.11 Indicate the type of PII to be accessed. If you requested a HIPAA waiver for screening only, indicate any additional PII types that will be used post-screening.

- Names
- Any geographic area smaller than a state
- Any date (except year) that is directly related to an individual and/or ages over 89
- Telephone numbers
- Fax numbers
- Email addresses
- Social Security Numbers (SSNs) or Scrambled SSNs
- Medical record numbers
- Health plan beneficiary numbers
- Account numbers
- Certificate and/or license numbers
- Vehicle ID and serial numbers including license plate numbers
- Device identifiers and serial numbers
- Web Universal Resource Locators (URLs)
- Internet protocol (IP) addresses
- Biometric identifiers, including finger & voice prints
- Full-face photographic images and any comparable images
- Any other unique identifiers (number, characteristic, or code)
- None of the above

Please explain the other unique identifier(s).

Other identifier is CDW PatientICN. Biometric identifiers refer to voice recordings collected during interviews.

13.12 Will this protocol include the use of Protected Health Information (PHI) that requires specific consent from subjects? If you requested a HIPAA waiver for screening only, indicate any PHI types that will be used post-screening.

- Alcoholism or alcohol abuse information
- Drug abuse information
- Sickle cell anemia information
- HIV test/infection results
- None of the above

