We will recruit up to 30 veterans with prediabetes to participate in the LC-DPP. The intervention will be delivered in partnership with VA Certified Diabetes Educators who will serve as lifestyle coaches for the group-based intervention. The LC-DPP lifestyle coaches will deliver 16-weekly one-hour group sessions over the first 6 months and 8 maintenance sessions over the subsequent 6 months. **Table 1** shows session topics. Participants will receive a binder to hold study materials. They will be provided with printed handouts on a session-by-session basis. Individuals that are absent for a particular session will receive corresponding session materials by e-mail or postal mail.

The CDC's Diabetes Prevention Program instructs participants to adhere to a fat-restricted diet with an explicit cap of less than 33-55 grams of fat per day depending on starting body weight. In contrast, LC-DPP participants will be initially instructed to follow *ad-libitum* very low-carbohydrate diet, which restricts carbohydrate intake (not including fiber) to 20-35 grams per day with the goal of achieving nutritional ketosis. Participants will be encouraged to eat a normal amount of protein (roughly 80-120 grams per day) and to derive the remaining calories from fat. Allowable foods include: meats, fish, poultry, eggs, cheese, seeds, nuts, leafy greens, non-starchy vegetables, and some fruits.

During the LC-DPP's maintenance phase, participants will be instructed to gradually reintroduce carbohydrates (e.g., 5 non-fiber grams of carbohydrates per week) if: (1) they have met their weight loss target and (2) if they desire to liberalize their carbohydrate intake.

To minimize potential side effects (e.g. headache, constipation, muscle cramps, diarrhea, general weakness, and rash) participants will be instructed to replace one meal a week with a low-carbohydrate alternative, starting with breakfast. Participants will be counseled to drink sufficient water and to consume adequate sodium. Further, primary care providers will be notified of their patients' involvement in this study, and they will be given a handout that describes the intervention, potential side effects, and strategies to minimize side effects.

Session Number	Topic
Core phase	
0	Study information session (Informed consent to be obtained)
1	Welcome to the Low-Carb Diabetes Prevention Program
2	Be a Carbohydrate Detective
3	Low-Carb Meals
4	Low-Carb Cooking and Shopping
5	Move Those Muscles

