Below is a list of reasons that people sometimes give for eating tasty foods and drinks such as:

- Sweets like chocolate, doughnuts, cookies, cake, candy, ice cream, other desserts.
- Salty snacks like chips, pretzels, and crackers.
- Fast foods like hamburgers, cheeseburgers, pizza, fried chicken and French fries.
- Sugary drinks like soda, sweet tea, milkshakes, and smoothies.

To forget y	Q3	1 =	Coping	Burgess,
Because it	Q4	Almost	score:	E. E.,
To cheer u	Q5	never/Ne	Average	Turan, B.,
To forget a	Q6	ver	of four	Lokken, K.
		2 = Some	responses	L., Morse,
		of the	.	A.. &

Energy Levels between Meals

In the past week, two hours after you ate BREAKFAST, how do you feel?

Alert	Q1	Answer	NA	NA
Energetic	Q2	choices 1		
Tired	Q3	through		
Brain fog o	Q4	7, with		
Food cravii	Q5	anchors		
Hunger	Q6	on 1, 7:		
Moodiness	Q7	1- Not at		
		all		
		7		

In the past week, two hours after you ate LUNCH, how do you feel?

Alert	Q8	Answer	NA	NA
Energetic	Q9	choices 1		
Tired	Q10	through		
Brain fod o	Q11	7, with		
Food cravii	Q12	anchors		
Hunger	Q13	on 1, 7:		
Moodiness	Q14	1- Not at		
		all		

Physical Symptoms

How often have you experienced the following over the past week?

Acne	Q1		NA	NA
Bad breath	Q2			
Bloating or	Q3			

Cold hands Q4
Constipation Q5
Diarrhea Q6
Dizziness Q7
Dry mouth Q8
Constant tiredness Q9
Food intolerance Q10

Headaches Q11

Heart palpitations or a racing heart Q12

Heartburn Q13

Joint or muscle pain Q14

Muscle cramps Q15

Nausea Q16

Trouble concentrating Q17

Weakness Q18

Hair loss Q19

Sexual problems Q20

Numbness (loss of sensation) in the feet, legs, or hands Q21

Tingling or prickling sensation in the feet, legs, or hands Q22

Not at all
1 day a week
2-3 days a week
4-5 days a week
6-7 days a week

Burning or shooting pain in the feet, legs, or hands

Q23

Blurred or deteriorating vision

Q24

Please describe any other psychological or physical symptoms that you experienced during the past month.

Q25

Participants may enter free text of whatever they choose.

Health
Global Health PROMIS Questionnaire:

Please respond to each item by marking one box per row

In	Q1	5-	Re-code:	PROMIS
In	Q2	Excellent	Q7 (pain	Health
general,		4- Very	on	Organizati
would		good	average):	on and
you say		3- Good	0 = 5	PROMIS
your		2- Fair	1,2,3 = 4	Cooperati
quality of		1- Poor	4,5,6 = 3	ve Group,
life is:			7,8,9 = 2	2008-
In	Q3		10 = 1	2012.
general,				https://w
how			Global	ww.iconq
would			Physical	uerms.org
you rate			Health	/sites/all/

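### The symptom checklist has no rash item, although the protocol names rash as a potential diet side effect and every other named side effect has an item

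*Protocol*

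**What the plan says.** The Intervention part of protocol section 5.1 gives the side effects that gradual introduction of the diet is meant to limit: "To minimize potential side effects (e.g. headache, constipation, muscle cramps, diarrhea, general weakness, and rash". The list is illustrative and the word used is potential. The Risks and Benefits part of the same section gives a second diet list, of constipation, headache, bad breath and muscle cramps.

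The surveys are a stated source of side-effect data. IRB form item 13.10 says that "these surveys will include self-reported side effects and experiences with the intervention", and protocol section 5.5 lists side effects among the survey domains at baseline, 6 months and 12 months. Section 5.5 also makes change in self-reported survey measures a secondary measure.

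The instrument is set out in the SAP. Its Physical Symptoms block opens with "How often have you experienced the following over the past week" and offers five frequency options. The closed items run from acne (Q1) to "Blurred or deteriorating vision" (Q24). Item Q25 is open: "Please describe any other psychological or physical symptoms that you experienced during the past month".

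**The concern.** A closed checklist prompts every respondent on every item, so each item yields a frequency at baseline and a change at 6 and 12 months. A symptom without an item yields data only from participants who think to mention it. If one named side effect is left to free text while the rest are prompted, it will tend to look rarer than they do for reasons of measurement alone. The abstract says that the data will inform a large comparative trial. A designer reading the checklist results would have figures for the other named side effects and nothing comparable for rash, and could take that silence as absence.

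**Working it through.** The documents state no rash rate or related figure, so there is nothing to reproduce. The check is a matching of lists.

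| Side effect | Named in protocol section 5.1 | SAP closed item |
|---|---|---|
| Headache | Intervention; Risks and Benefits | "Headaches Q11" |
| Constipation | Intervention; Risks and Benefits | "Constipation Q5" |
| Muscle cramps | Intervention; Risks and Benefits | "Muscle cramps Q15" |
| Diarrhea | Intervention | Q6 |
| General weakness | Intervention | Q18 |
| Rash | Intervention | none |
| Bad breath | Risks and Benefits | Q2 |

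Coverage is 5 of 6 on the Intervention list alone, and 6 of 7 on the two lists together. Rash is the only gap either way. The one skin item is acne.

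Could PDF extraction have hidden a rash item? Some labels in the block are cut, but the cut ones still show about ten characters. Acne shows only four, so a longer label that began with that word would show more of it. Nothing visible suggests a rash item.

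The remaining routes by which rash could be recorded are:

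- **Q25 free text.** Unprompted, with a past-month window against the checklist's past week.
- **Open Ended Diet, Q2 (SAP).** Free text on what about the participant's health got worse on the food plan. Also unprompted.
- **Interviews (protocol section 5.5; IRB form 6.42).** Side effects are an example topic. The sample is purposive by weight-loss outcome (14 in section 5.5, up to 30 in item 6.42) and the interviews are optional (item 13.10), so they cannot give a rate.
- **Spontaneous report** to study staff, study physicians or the primary care provider.

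The qualitative analysis plan (protocol section 5.6 and SAP) covers interviews. It gives no coding rule for survey free text.

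A purely illustrative calculation shows how the loss would behave. Let r be the share of participants with a rash inside the recall window at a survey, and s the share of those who volunteer it. Both are assumed. With n = 30, the protocol's maximum, and all responding, expected reports = 30 × r × s and P(no report) = (1 − r × s)^30.

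| r | s = 0.25 | s = 0.50 | s = 0.75 | s = 1 |
|---|---|---|---|---|
| 5% | 0.38; 0.69 | 0.75; 0.47 | 1.12; 0.32 | 1.5; 0.21 |
| 10% | 0.75; 0.47 | 1.5; 0.21 | 2.25; 0.10 | 3.0; 0.04 |
| 20% | 1.5; 0.21 | 3.0; 0.04 | 4.5; 0.01 | 6.0; 0.001 |

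Each cell gives expected reports, then P(no report). The s = 1 column describes a closed item only if it catches every case in its window. The checklist and Q25 have different windows, so r need not be the same for both. The spread across the table shows that no single figure can be defended.

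**The case against.** The strongest reply is that the plan contains no estimate for this gap to bias. A reader might infer that a participant with rash would be scored as having no listed symptom, or that a rash rate would be pulled toward zero. The documents support neither. The scoring entry for the Physical Symptoms block is NA, no any-symptom score is defined, and no rash rate is a planned outcome. Primary outcomes are feasibility and acceptability.

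A reader might also infer that the team expects rash, or that Q25 is the only place to report it. The protocol says potential, and rash is absent from the diet-risk lists in IRB form 9.1 and in section 5.1 under Risks and Benefits. The Open Ended Diet question is a second free-text route tied directly to the diet, and this mixed-methods study also has its interviews.

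Finally, a closed item would not capture every rash. The checklist covers one week at 0, 6 and 12 months, and section 5.1 says the diet symptoms it lists under Risks and Benefits usually resolve within the first couple of weeks. That list omits rash, but an early, short-lived rash would be missed with or without the item.

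All of this stands, and it limits the size of the point. It does not remove the asymmetry. Timing affects every checklist item alike, whereas only rash among the named side effects lacks a prompt. The other routes rely on the participant raising it, and none yields a baseline frequency or a change.

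**Conclusion.** The point holds as a minor gap in measurement. One of the six side effects in the Intervention list (one of seven across both section 5.1 lists) has no prompted frequency, no baseline value and no change score. It is likely to be under-ascertained relative to the prompted ones. That rests on the usual assumption that people report less when not asked; the documents give neither a rash frequency nor a free-text reporting rate, so the amount is unknown and the table above is not an estimate of it. No primary outcome, named endpoint or decision rule changes. This is a cheap improvement to the tolerability data that the pilot passes on.

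**What to change.** - Add a rash item to the Physical Symptoms checklist, with the same past-week frequency options, in the baseline, 6-month and 12-month surveys.
- Leave Q25's past-month window as it is. Shortening it to match the checklist would narrow an existing route for reporting rash.
- For surveys already completed, specify that Q25 and the Open Ended Diet answers on what got worse will be coded for rash. Report the result as spontaneous-only, apart from the checklist frequencies.
- State in the SAP and in any report that a past-week checklist at 0, 6 and 12 months will miss early transient side effects, rash included.

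The cost is one extra survey line, a small IRB amendment, a short free-text coding task, and no baseline value for participants surveyed before the change.
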